8.2.5 Serious Adverse Event Onset and Resolution Dates

The onset date of the SAE is defined as the date the event meets serious criteria. The resolution date is the date the event no longer meets serious criteria, the date the symptoms resolve, or the

event is considered chronic. In the case of hospitalizations, the hospital admission and discharge dates are considered the onset and resolution dates, respectively.

In addition, any signs or symptoms experienced by the subject after signing the informed consent/assent form, or leading up to the onset date of the SAE, or following the resolution date of the SAE, must be recorded as an AE, if appropriate.

8.2.6 Fatal Outcome

Any SAE that results in the subject's death (ie, the SAE was noted as the primary cause of death) must have fatal checked as an outcome with the date of death recorded as the resolution date. For all other events ongoing at the time of death that did not contribute to the subject's death, the outcome should be considered not resolved, without a resolution date recorded.

For any SAE that results in the subject's death or any ongoing events at the time of death, unless another investigational product action was previously taken (eg, drug interrupted, reduced, withdrawn), the action taken with the investigational product should be recorded as "dose not changed" or "not applicable" (if the subject never received investigational product). The investigational product action of "withdrawn" should not be selected solely as a result of the subject's death.

8.2.7 Regulatory Agency, Institutional Review Board, Ethics Committee, and Site Reporting

IQVIA Services Japan K.K. is responsible for notifying the relevant regulatory authorities/central institutional review boards (IRBs)/ethics committees (ECs) of related, unexpected SAEs. In addition the sponsor and/or designee is responsible for notifying active sites of all related, unexpected SAEs occurring during all interventional studies across the teduglutide program.

The investigator is responsible for notifying the local IRB or the relevant local regulatory authority of all SAEs that occur at his or her site as required.

8.3 Adverse Events of Special Interest

An AE of special interest is an AE (serious or nonserious) of scientific and medical concern specific to the sponsor's product or program and for which ongoing monitoring and immediate notification by the investigator to the sponsor is required.

The AEs of special interest that require expedited regulatory reporting for this study include the following:

- Growth of pre-existing polyps of the colon
- Benign neoplasia of the GI tract including the hepatobiliary system
- Tumor-promoting ability (eg, benign and/or malignant neoplasia of any kind, not limited to those of the GI or hepatobiliary system)

For AEs of special interest, IQVIA Services Japan K.K. must be informed within 24 hours of first awareness as per the SAE notification instructions described in Section 8.2.2 even if the event does not fulfill seriousness criterion.

8.4 Dose Interruption of Individual Subjects

The investigator is responsible for contacting the sponsor or designee when the subject's daily investigational product dosing regimen is interrupted. Attempts should be made to contact the sponsor or designee prior to dose interruption. Reasons for dosage interruption may include but are not limited to such as hospitalization and AEs, a lapse in investigational product delivery, etc.

Investigational product must be discontinued if any of the following events occur:

- Pregnancy
- Severe hypersensitivity, such as anaphylaxis determined by the investigator to be related to the investigational product. This does not include the presence of anti-teduglutide antibodies, mild injection site reactions or mild symptoms that according to the investigator do not pose a significant risk to the subject.
- An AE listed in Table 6 that is of NCI CTCAE severity Grade 3 or 4 and considered to be related to the investigational product administration (see Section 8.4.1)
- Confirmed drug-induced liver injury (DILI) related to teduglutide (see Section 8.4.2)

8.4.1 Dose Interruption Criteria Based on Known Risks of Teduglutide

The investigational product may be discontinued if the subject experiences an AE listed in Table 6 that is of severity \geq Grade 3 per the NCI CTCAE. All such AEs should be discussed with the medical monitor or designee as soon as possible. Teduglutide administration must be discontinued if the AE is considered related to the investigational product. The length of dose interruption, and whether teduglutide administration resumes or is permanently discontinued, depends on the clinical situation.

Investigators and the DMC should be guided by the descriptions of Grade 3 and 4 events, as they relate to identified risks associated with the administration of teduglutide (see Table 6).

Adverse Event	Grade 3 Description	Grade 4 Description
Gastrointestinal Disorders	\$	
Colorectal polyps	Severe or medically significant but not immediately life threatening; hospitalization or prolongation of existing hospitalization indicated; disabling; limiting self-care activities of daily living	Life-threatening consequences; urgent intervention indicated
Intestinal obstruction	Hospitalization indicated; elective operative intervention indicated; limiting self-care activities of daily living; disabling	Life-threatening consequences; urgent operative intervention indicated
Gallbladder and Bile Duc	Disease	
Cholecystitis	Severe symptoms; radiologic, endoscopic or elective operative intervention indicated	Life-threatening consequences; urgent operative intervention indicated
Gallbladder perforation	Not Applicable	Life-threatening consequences; urgent intervention indicated
Gallbladder obstruction	Symptomatic and severely altered gastrointestinal function; tube feeding, total parenteral nutrition or hospitalization indicated; nonemergent operative intervention indicated	Life-threatening consequences; urgent operative intervention indicated
Gallbladder infection	Intravenous antibiotic, antifungal, or antiviral intervention indicated; radiologic, endoscopic, or operative intervention indicated	Life-threatening consequences; urgent intervention indicated
Alkaline phosphatase increased	>5.0 to 20.0x ULN	>20.0x ULN
Blood bilirubin increased	>3.0 to 10.0x ULN	>10.0x ULN
Bile duct stenosis	Severely altered gastrointestinal function; radiologic, endoscopic or elective operative intervention indicated	Life-threatening consequences; urgent operative intervention indicated
Pancreatic Disease		
Pancreatitis	Severe pain; vomiting; medical intervention indicated (eg, analgesia, nutritional support)	Life-threatening consequences; urgent intervention indicated
Pancreatic duct stenosis	Severely altered gastrointestinal function; tube feeding or hospitalization indicated; elective operative intervention indicated	Life-threatening consequences; urgent operative intervention indicated
Pancreas infection	Intravenous antibiotic, antifungal, or antiviral intervention indicated; radiologic or operative intervention indicated	Life-threatening consequences; urgent intervention indicated
Serum amylase increased ^a	>2.0 to 5.0x ULN	>5.0x ULN
Lipase increased ^a	>2.0 to 5.0x ULN	>5.0x ULN

Table 6 Adverse Events that May Lead to Dose Interruption

Adverse Event	Grade 3 Description	Grade 4 Description
Cardiovascular Disease		
Heart failure	Severe with symptoms at rest or with minimal activity or exertion; intervention indicated	Life-threatening consequences; urgent intervention indicated (eg, continuous intravenous therapy or mechanical hemodynamic support)

Table 0 Auverse Events that May Deau to Dose Interruptio	Table 6	Adverse Events that	May Lead to	Dose Interruption
--	---------	---------------------	-------------	--------------------------

Source: Common Terminology Criteria for Adverse Events, version 4.03, 14 June 2010

ULN=upper limit of normal

^a In the setting of clinically acute and symptomatic pancreatitis

8.4.2 Dose Interruption Criteria Based on Drug-induced Liver Injury

Teduglutide administration for an individual subject may need to be discontinued if the subject has clinical and laboratory evidence of potential DILI, in the absence of an alternative explanation, as identified by the following criteria:

- Subjects with normal (or low) values of ALT and AST at baseline:
 - ALT or AST >8x ULN
 - ALT or AST >5x ULN for more than 2 weeks
 - ALT or AST >3x ULN and (total bilirubin >2x ULN or INR>1.5)
 - ALT or AST >3x ULN with the appearance of fatigue, nausea, vomiting, right upper quadrant pain or tenderness, fever, rash, and/or eosinophilia (>5%)
- Subjects with baseline elevations of values of ALT and/or AST over ULN:
 - ALT or AST >8x ULN
 - ALT or AST >5x ULN and >2x baseline value for more than 2 weeks
 - (ALT or AST >3x ULN and >2x baseline value) and (total bilirubin >2x ULN or INR>1.5)
 - ALT or AST >3x ULN and >2x baseline value with the appearance of fatigue, nausea, vomiting, right upper quadrant pain or tenderness, fever, rash, and/or eosinophilia (>5%)

All laboratory values suggestive of potentially new DILI should be repeated and verified within 3 days. INR should be measured with this set of verification laboratory assessments and an inquiry should be made as to the presence of clinical symptoms consistent with new liver injury. The subject should be followed closely to determine the trajectory of the laboratory abnormalities and to evaluate the cause of liver injury. This evaluation may include, as clinically indicated, consideration of sepsis, acute viral hepatitis (eg, hepatitis A immunoglobulin M [IgM], hepatitis B surface antigen, hepatitis C antibodies, cytomegalovirus IgM, Epstein-Barr virus antibody panel), hepatobiliary obstruction (ultrasound), autoimmune hepatitis (anti-nuclear, anti-smooth muscle, anti-actin, or anti-liver kidney microsomal antibodies), intestinal failure associated liver disease, cardiovascular causes such as ischemic hepatitis, and concomitant hepatotoxic treatments.

CONFIDENTIAL

Additional evaluations may be performed at the discretion of the investigator in consultation with the medical monitor or designee.

Teduglutide administration must be discontinued if DILI is confirmed and deemed related to investigational product.

8.5 Early Termination of the Clinical Study

The DMC may recommend stopping the study if:

- At least 2 subjects develop the same event listed in Table 6 of severity CTCAE Grade 3
- or
- 1 subject develops an event listed in Table 6 of severity CTCAE Grade 4 which is attributable to investigational product or is not reasonably related to the underlying disease process.

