8.1.1 Severity Categorization

The severity of AEs must be recorded during the course of the event including the start and stop dates for each change in severity. An event that changes in severity should be captured as a new event. Worsening of pre-treatment events, after initiation of investigational product, must be recorded as new AEs (for example, if a subject experiences mild intermittent dyspepsia prior to dosing of investigational product, but the dyspepsia becomes severe and more frequent after first dose of investigational product has been administered, a new AE of severe dyspepsia [with the appropriate date of onset] is recorded on the appropriate eCRF).

The medical assessment of severity is determined by using the following definitions:

Mild: A type of AE that is usually transient and may require only minimal treatment or therapeutic intervention. The event does not generally interfere with usual activities of daily living.
 Moderate: A type of AE that is usually alleviated with specific therapeutic intervention. The event interferes with usual activities of daily living, causing discomfort but poses no significant or permanent risk of harm to the research subject.
 Severe: A type of AE that interrupts usual activities of daily living, or significantly affects clinical status, or may require intensive therapeutic intervention.

Shire SHP633-302 Protocol Amendment 4 Teduglutide

Note that the severity of AEs listed in Table 6 that may lead to dose interruption based on known risks of teduglutide will also be evaluated using the National Cancer Institute's (NCI) Common Terminology Criteria for Adverse Events (CTCAE) grading criteria (Section 8.4.1).

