9.4.2 Data Monitoring Committee

The DMC for this study will be conducted in accordance with the FDA Guidance for Clinical Trial Sponsors: Establishment and Operation of Clinical Trial Data Monitoring Committees (March 2006).

The DMC will be an external, independent board comprised of physicians with relevant training. The DMC will be restricted to individuals free of significant conflicts of interest, including, but not limited to, financial, scientific, or regulatory in nature. The DMC will be governed by a Charter agreed to by members of the Committee and the sponsor. Members of the Committee may not be study investigators or be employed at the same institution as a study investigator, individuals employed by Shire, independent contractors hired by Shire, or members of regulatory agencies. The DMC may make recommendations to Shire regarding stopping, modifying or continuing the study; however, Shire will have the final responsibility to determine whether the study should be modified or temporarily or permanently stopped.

Safety and tolerability results will be evaluated by a DMC which will convene approximately every 3 months during the active study period (date of the first subject's first dose to date of the last subject's last dose), based on subject enrollment. The DMC review will include all cumulative safety data from study assessment through the end of each review period.

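### Section 8.5 counts two same-event Grade 3 cases towards stopping, but not the same pair when one or both are instead Grade 4 ascribed to the underlying disease

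*Protocol*

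**What the plan says.** Section 8.5 (Early Termination of the Clinical Study, Amendment 4) opens with "The DMC may recommend stopping the study if" and lists two alternatives.

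- First: "At least 2 subjects develop the same event listed in Table 6 of severity CTCAE Grade 3". No condition on cause is attached, and Grade 4 is not mentioned.
- Second: "1 subject develops an event listed in Table 6 of severity CTCAE Grade 4 which is attributable to investigational product". A Grade 4 event with no reasonable link to the underlying disease qualifies as well. One subject suffices, but a Grade 4 that is put down to the disease does not count.

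Elsewhere the protocol names both grades when it means both. Section 8.4 requires discontinuation for "An AE listed in Table 6 that is of NCI CTCAE severity Grade 3 or 4 and considered to be related", meaning related to the product. Section 8.4.1 uses a threshold of Grade 3 or above for possible discontinuation, and also says "Investigators and the DMC should be guided by the descriptions of Grade 3 and 4 events". Table 6 defines the grades as separate bands; for blood bilirubin, Grade 3 is >3.0 to 10.0x ULN and Grade 4 is >10.0x ULN.

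**The concern.** A stopping criterion should not become harder to meet as events get worse. Here a pair of matching Grade 3 events qualifies with no question about cause. Make one of them a Grade 4 ascribed to the disease and it drops out of the first criterion because of its grade, and out of the second because of its attribution.

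The first criterion is the only one in Section 8.5 without an attribution test. It is therefore the only one that can pick up a repeated event whose case-by-case attribution to disease is mistaken. That matters in this population. Section 8.1.2 defines a related event as one that the subject's medical condition cannot explain, so attribution to disease is easily reached. Section 1.1 names liver disease as a complication of long-term parenteral support, and Table 6 includes bilirubin and alkaline phosphatase. Exclusion criterion 20 excludes infants for hepatic impairment only when at least 2 of 5 listed findings are present, so an infant with persistent cholestasis alone can enrol. With planned minimums of 5 children and 2 infants, two matching severe events are a large part of the evidence.

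**Working it through.** The protocol states no figure for this rule, so there is none to reproduce. The check is a full enumeration.

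**Inputs.** The two criteria are from Section 8.5, the grade definitions from Table 6, and the recording rule from Section 8.1.1.

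**States.** Take two subjects with the same Table 6 event. Each case is Grade 3 or 4, and is either D (ascribed to the underlying disease) or Q (product-attributable, or not reasonably disease-related). That gives four states: 3Q, 3D, 4Q, 4D. The number of unordered pairs is 4 × 5 / 2 = 10.

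**Rule as written.** Met if both cases are Grade 3, or if either is 4Q.

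**Rule with Grade 3 or higher in the first criterion.** Met if both cases are Grade 3 or above, or if either is 4Q.

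| Pair | As written | Revised |
|---|---|---|
| 3Q, 3Q | met (first) | met |
| 3Q, 3D | met (first) | met |
| 3D, 3D | met (first) | met |
| 3Q, 4Q | met (second) | met |
| 3D, 4Q | met (second) | met |
| 4Q, 4Q | met (second) | met |
| 4Q, 4D | met (second) | met |
| 3Q, 4D | **not met** | met |
| 3D, 4D | **not met** | met |
| 4D, 4D | **not met** | met |

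As written, 7 of 10 pairs meet the rule; revised, 10 of 10.

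**Reversals.** Hold attribution fixed and raise the grade. The moves from 3Q,3D to 3Q,4D, from 3D,3D to 3D,4D, and from 3D,3D to 4D,4D each go from met to not met. Under the revised rule none do.

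**Exception.** Section 8.1.1 says "An event that changes in severity should be captured as a new event". A subject with a separately recorded Grade 3 phase before Grade 4 could still count towards the first criterion. The gap concerns events with no such record.

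**Table 6.** It lists 15 events. For 14 a Grade 3 level is defined; for gallbladder perforation it is marked as not applicable. That event can never meet the first criterion, though one product-attributable case meets the second.

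**Illustration on assumed rates.** The protocol gives no event rates, so these are assumptions. Take 5 + 2 = 7 subjects, independent, one event type, no separate Grade 3 record for a Grade 4 case, and no 4Q case. The chance that at least 2 subjects count is 1 − (1−p)^7 − 7p(1−p)^6. As written, p is the Grade 3 risk; revised, p adds the disease-ascribed Grade 4 risk.

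| Grade 3 risk | Disease-ascribed Grade 4 risk | As written | Revised |
|---|---|---|---|
| 5% | 5% | 0.044 | 0.150 |
| 10% | 5% | 0.150 | 0.283 |
| 10% | 10% | 0.150 | 0.423 |

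The finding does not depend on these values.

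**The case against.** The strongest reply is that nothing turns on the wording. Section 8.5 lists occasions on which the DMC may act; it obliges nothing and does not say these are the only grounds. Section 9.4.2 adds "The DMC may make recommendations to Shire regarding stopping, modifying or continuing the study" and has the DMC review all cumulative safety data, while Section 10.1.4 lets the sponsor stop at any time. Nor would a Grade 4 pass unseen. For most Table 6 events it means life-threatening consequences, hence a serious event reported within 24 hours, and Section 8.4.1 sends every Table 6 event of Grade 3 or above to the medical monitor. A committee of physicians would hardly treat a Grade 4 case as falling short of Grade 3. Finally, 7 of 10 counts logical cases, not probabilities.

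Most of this stands as a limit on harm, including the point about the count. It does not make the rule coherent. Reading Grade 3 as Grade 3 or worse has to set aside Sections 8.4 and 8.4.1, which write the wider form where it is meant. If the wider form was intended here too, the same edit is needed.

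One could also argue that the attribution clause governs both criteria. Disease-ascribed Grade 3 events would then not count either, and the reversals would vanish. The layout is against this: the clause sits in the second bullet only.

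**Conclusion.** The concern holds: the rule is wrong as written. Three of the 10 same-event pairs fail Section 8.5, all three contain a disease-ascribed Grade 4, and each has a lower-grade counterpart that passes. This rests on the literal text of the two bullets, on no separate Grade 3 record existing for the Grade 4 case, and on no other Grade 4 qualifying. The DMC charter is not at hand and might repair the gap.

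The practical weight is modest, since no one's authority to stop is removed and no endpoint, analysis or subject-level discontinuation rule is affected. It should still be corrected, because a written safety criterion in a paediatric trial ought to be ordered by severity.

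**What to change.** In the first bullet of Section 8.5, replace Grade 3 with *Grade 3 or higher*, so that it covers at least 2 subjects with the same Table 6 event at that level. Leave the second bullet as it is, and align the DMC charter. This also brings gallbladder perforation within reach of the first criterion.

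The cost is one phrase in the protocol and one line in the charter, with no extra data or staff. The downside is that the criterion will be met more often, including by Grade 4 events that really are due to the disease. How much more often depends on event rates the protocol does not give. Because the criterion stays permissive, no stop is forced.

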9 DATA MANAGEMENT AND STATISTICAL METHODS

9.1 Data Collection

The investigator or investigators' authorized site personnel must enter the information required by the protocol in the eCRF. A study monitor will visit each site in accordance with the monitoring plan and review the eCRF data against the source data for completeness and accuracy. Discrepancies between source data and data entered on the eCRF will be addressed by the investigator or qualified site personnel. When a data discrepancy warrants correction, the correction will be made by the investigator or authorized site personnel. The investigator must verify that all data entries in the eCRF are accurate and correct. Original diary data should be entered into the eCRF and take precedence over data collected over the phone. Data collection procedures will be discussed with the site at the site initiation visit and/or at the investigator's meeting. Once a subject is enrolled, it is expected that the investigator or authorized site personnel will complete the eCRF entry in a timely manner following the subject's visit.

9.2 Clinical Data Management

Training will occur at an Investigator meeting or at the site initiation visit or both, and instruction manuals will be provided to aid consistency in data collection and reporting across sites.

The required data will be captured in a validated clinical data management system that is compliant with the US Food and Drug Administration (FDA) 21 CFR Part 11 Guidance. The clinical trial database will include an audit trail to document any evidence of data processing or activity on each data field by each user.

Data will be entered into a clinical database as specified in the Data Management Plan. Quality control and data validation procedures will be applied to ensure the validity and accuracy of the clinical database. Users will be trained and given restricted access, based on their role(s) in the study, through a password-protected environment.

Data will be reviewed and checked for omissions, errors, and values requiring further clarification using computerized and manual procedures. Data queries requiring clarification will be communicated to the site for resolution. Only authorized personnel will make corrections to the clinical database, and all corrections are documented in an auditable manner.

Serious adverse event information captured in the clinical trial database will be reconciled with the information captured in the Shire Global Drug Safety database.

